# 8.3.1. Secondary Safety Endpoints

Secondary safety endpoints include the following:

- 1. All Grade 3-5 adverse events, as defined by the NCI–CTCAE system, which are defined as possibly, probably, or definitely related to SLE.
- 2. All Grade 3-5 adverse events, as defined by the NCI-CTCAE system, which are defined as possibly, probably, or definitely related to MMF.
- 3. All NCI-CTCAE Grade 3-5 adverse events.
- 4. All serious adverse events.
- 5. All infection related events.
- 6. All malignancies.
- 7. All NCI-CTCAE Grade 3-5 hematological events.
- 8. Mortality possibly, probably, or definitely related to SLE.
- 9. All-cause mortality, defined as any death occurring at any time after randomization.

Serious adverse events will include only those events deemed serious per 21 CFR 312.32 (See Protocol Section 7.2.4). Events that require 24-hour reporting to the sponsor, such as BILAG A and severe SELENA-SLEDAI flares, will not be included unless they also meet SAE reporting criteria per 21 CFR 312.32; these events will be summarized separately.

Infections will include those events that are coded to the SOC of "Infections and infestations" along with any AE with an answer of Yes to the question "Was this AE an infection?" on the Adverse Events CRF page.

Malignancies will include those events that are coded to the SOC of "Neoplasms benign, malignant and unspecified (incl cysts and polyps)" along with any AE with an answer of Yes to the guestion "Was this AE a malignancy?" on the Adverse Events CRF page.

Hematological events will include AEs that are coded to the SOC of "Blood and lymphatic system disorders".

For each of the safety endpoints listed above, the AEs, classified by MedDRA system organ class and preferred term, will be summarized for each treatment group and overall. The

Version: 1.0 Page 32 of 48

summaries will include the event rate (i.e. number of events per person-time) in addition to the number and percent of events and subjects experiencing events.

The proportion of subjects experiencing at least one event specified above in each treatment group will be reported and the treatment groups compared based on Fisher's Exact Test. In addition, event rates in the two arms will be compared using Poisson regression.

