### 5.4.1 Malignancy

Increased risk of lymphoproliferative disease and non-melanoma skin cancers will be addressed by the physical examinations conducted at each visit. If evidence of lymphoproliferative disease emerges, work up will be guided by the institution's standard of care requirements. If malignancy (other than skin cancers described below) is diagnosed, the study drug will be discontinued and the subject will be treated according to standard of care per institutional requirements. If new non-melanoma skin cancer is found and fully treatable with local procedures, the subject may continue in the trial as planned based on investigator discretion.

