#### 7.3.4 **Recording Adverse Events**

Throughout the study, the investigator will record and grade adverse events NCI-CTCAE grade 2 and above on the appropriate AE electronic case report form (AE eCRF) regardless of their severity or relation to study medication or study procedure.

Once recorded, an AE will be followed until it resolves with or without sequelae, or until the end of study participation, or until 30 days after the subject prematurely withdraws (without withdrawing consent)/or is withdrawn from the study, whichever occurs first.

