### System Lupus International Collaborating Clinics/ACR Damage Index for SLE (SLICC/DI\*)

Check "Present" if descriptor is present at the time of visit (and circle 2 if applicable)

Damage (nonreversible change, not related to active inflammation) occurring since onset of lupus, ascertained by clinical assessment and present for at least **6 months** unless otherwise stated. Repeat episodes must occur 6 months apart to score 2. The same lesion cannot be scored twice.

	Descriptor	Definition	Present	Score
		Claudication for 6 months		1
		Minor tissue loss (pulp sauce)		1
6	Peripheral vascular			1 (2)
		Venous thrombosis with swelling, ulceration, or venous stasis		1
		Infarction or resection of bowel below duodenum spleen, liver, or gall bladed ever, for cause any (score $2 \text{ if} > 1 \text{ site}$ )		1 (2)
7	Gastrointestinal	Mesenteric insufficiency		1
		Chronic peritonitis		1
		Stricture or upper gastrointestinal tract surgery ever		1
	Musculoskeletal	Muscle atrophy or weakness		1
		Deforming or erosive arthritis (including reducible deformities, excluding avascular necrosis)		1
8		Ausculoskeletal         Osteoporosis with fracture or vertebral collapse (excluding avascular necrosis)		1
		Avascular necrosis (score 2 if $>$ 1)		1 (2)
		Osteomyelitis		1
		Scarring chronic alopecia		1
9	Skin	Skin Extensive scarring or panniculum other than scalp and pulp space		1
		Skin ulceration (excluding thrombosis) for > 6 months		1
10		Premature gonadal failure		1
11		Diabetes (regardless of treatment)		1
12	Maligna	incy (exclude dysplasia) (score 2 if $> 1$ site)		1 (2)
		Total Score (sum of scores next to descriptors marked	l present):	

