# 7.3.8. The Addition of Aggressive Adjunctive Therapy to MMF or Change in MMF Therapy to Cytotoxic Drug Due to Flare

**Endpoint**: Medications are assessed at each study visit throughout the duration of the study and are collected on the *Prior/Concomitant Medications* CRF page.

For both the maintenance and withdrawal arms, the addition of aggressive adjunctive therapy can include IV immunoglobulin or rituximab at any point during the subject's participation in the study. A change in therapy to cytotoxic drug due to flare can include drugs such as cyclophosphamide, etc. A blinded list of study medications will be reviewed to identify the addition of aggressive adjunctive therapy or cytotoxic drugs.

For each subject, a yes/no variable will be created to indicate whether a subject added aggressive adjunctive therapy to MMF or changed MMF therapy to cytotoxic drug due to flare by Week 60. Subjects off MMF in the withdrawal arm will be included in the endpoint if aggressive adjunctive therapy or cytotoxic drugs were added to treat a flare. Subjects who terminate early from the study prior to adding aggressive adjunctive therapy to MMF or changing MMF therapy to cytotoxic drug due to flare will be categorized as not meeting the endpoint.

The probability of adding aggressive adjunctive therapy to MMF or changing MMF therapy to cytotoxic drug due to flare will be calculated for each study arm.

**Analysis**: Analyses analogous to those specified for the primary endpoint (effect estimates and 95% confidence intervals, risk difference, and summaries of increased risk ( $\alpha$ ) vs.% confidence the "true" risk is  $\leq \alpha$ ) will be performed for adding aggressive adjunctive therapy to MMF or changing MMF therapy to cytotoxic drug due to flare by Week 60. See Section 7.2.2, *Primary Analysis of the Primary Endpoint*, for more details on the analyses. Additionally, type of new therapy will be summarized by treatment arm and overall.

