#### 8.3. Adverse Events

All AEs will be classified by system organ class (SOC) and preferred term, according to a standardized thesaurus (Medical Dictionary for Regulatory Activities [MedDRA] version 16.1). The severity of AEs will be classified using the National Cancer Institute's (NCI's) Common Toxicity Criteria for Adverse Events (CTCAE) version 4.0. Each AE is entered on the electronic case report form (eCRF) once at the highest severity. As such, no additional data manipulation is needed to identify events.

Adverse events will be collected from the time the subject signs the informed consent until he/she initiates study intervention or until he/she is determined to be ineligible to receive study intervention, if the investigator determines that the AE is related to a study-mandated procedure, treatment, or change in treatment.

Regardless of whether the above is applicable, for all participants: AEs will be collected from the time of initiation of study intervention (i.e., the administration of the first dose of study-supplied MMF as defined in Protocol Section 6.4.2, *Baseline/Randomization Visit*) until he/she completes study participation or until 30 days after he/she prematurely withdraws (without withdrawing consent) or is withdrawn from the study.

Treatment-emergent AEs will be identified as those with an onset date on or after the first dose of study medication as well as those with onset before first dose but that continued and worsened in severity after first dose. If the start of the AE in relation to the start of study medication cannot be established (e.g., the start date for the AE is missing), then the AE will be considered treatment-emergent. All data tabulations will be of only treatment-emergent events while non-treatment-emergent AEs will be listed separately, unless otherwise noted.

Indicator variables will be derived for the following categories of AEs: infections, malignancies, BILAG A flares, and severe SELENA-SLEDAI flares. Yes/no questions for each of these types of events are included on the *Adverse Events* CRF page.

Relationship to study treatment will be categorized as either treatment related (possibly, probably, or definitely related to study medication) or unrelated (unlikely related or unrelated).

An overall summary table will be developed to report the number of events and the number and percentage of subjects having at least one event in the following categories:

- AEs
- AEs indicated as serious

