- AEs that lead to study drug discontinuation
- AEs with an outcome of death
- AEs that were reported as being related to MMF
- AEs that were reported as being related to SLE
- AEs reported by maximum severity
- AEs that are BILAG A flares
- AEs that are severe SELENA-SLEDAI flares

Version: 1.0 Page 31 of 48

In addition, AEs classified by MedDRA SOC and preferred term will be summarized for each treatment group and overall for each of the following:

- All AEs
- AEs by maximum severity
- AEs by relationship to study drug

Summary tables will present the total number of events as well as the number and percentage of subjects experiencing the events. If a subject experiences the same AE on multiple occasions, the event will be counted once for each occurrence when reporting the number of AEs. When reporting the number of subjects experiencing the events, a subject will only be counted once if they experience an event within the particular SOC or preferred term. Percentages will be based on the number of subjects in the safety population. To account for differential duration of study participation among subjects, the summaries will include the event rate (i.e. number of events per person-time) in addition to the number and percent of events and subjects experiencing events.

Separate data listings will be provided for treatment-related AEs and AEs leading to study drug discontinuation.

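### SAP 8.3.1 builds the All malignancies endpoint from the whole MedDRA neoplasm class, so a benign or unspecified lesion counts as a malignancy even when the investigator answered No

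*SAP*

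**What the plan says.** Protocol 3.3.2 and SAP 8.3.1 both list All malignancies as a secondary safety endpoint. The protocol gives no derivation. SAP 8.3.1 supplies one: "Malignancies will include those events that are coded to the SOC of" "Neoplasms benign, malignant and unspecified (incl cysts and polyps", and it adds any event with a Yes to the malignancy question on the Adverse Events CRF page.

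Three other rules limit which events can enter:

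- Protocol 7.3.4: "the investigator will record and grade adverse events NCI-CTCAE grade 2 and above". Grade 1 events are not recorded.
- SAP 8.3: "All data tabulations will be of only treatment-emergent events", unless otherwise noted.
- SAP 8.3, on repeat events in one subject: "the event will be counted once for each occurrence when reporting the number of AEs".

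SAP 8.3 also plans an indicator variable for malignancies and notes the CRF yes/no item, but it does not make that item decisive. For each safety endpoint, SAP 8.3.1 plans tables by system organ class (SOC) and preferred term with person-time rates, a Fisher's exact test on subjects with at least one event, and a Poisson regression on event rates.

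**The concern.** The SOC's own title says that it holds benign and unspecified lesions, cysts and polyps. An endpoint built from the whole class is therefore a neoplasm endpoint carrying a malignancy label. The investigator's answer could separate the two, but the rule uses it only to add events.

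Malignancy is one of the MMF risks that the protocol sets against the risk of flare (Protocol 1.4 and 1.5), so readers will look at this comparison when weighing withdrawal. The overall adverse-event summary table in SAP 8.3 has no malignancy row, which leaves SAP 8.3.1 as the only planned between-arm comparison of malignancy. True malignancies are likely to be few with about 60 subjects per arm over 60 weeks, and with small counts one misclassified event can double the reported figure. Because each occurrence counts as an event, repeat lesions in one subject affect the rate more than the proportion.

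**Working it through.** The documents state no figure for this endpoint, so there is none to reproduce. The check has two parts: the logic of the rule, then the arithmetic of one misclassified event.

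**Logic.** The rule is: counted = (coded to the neoplasm SOC) OR (CRF malignancy question = Yes).

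| Coded to neoplasm SOC | CRF answer | Counted as malignancy |
|---|---|---|
| Yes | Yes | Yes |
| Yes | No | Yes |
| No | Yes | Yes |
| No | No | No |

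The second row is the problem. The last row bounds it: a benign lesion coded elsewhere and answered No is not counted. The grade and treatment-emergence limits reduce how many events arrive, but neither separates benign from malignant. Nothing in SAP section 8 narrows the SOC by preferred term, review or adjudication, and SAP section 12 does not mention the point.

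**Comparison within SAP 8.3.1.** Infections use the same construction (an SOC plus CRF Yes), but there the SOC title matches the label. For serious adverse events the section takes the stricter course: flares reported within 24 hours that do not meet the regulatory definition are kept out and summarised separately.

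**Comparison with the protocol.** Section 5.4.1, headed Malignancy, opens with: "Increased risk of lymphoproliferative disease and non-melanoma skin cancers will be addressed by the physical examinations conducted at each visit". The malignancy item of the SLICC/DI (Appendix D) carries the instruction "exclude dysplasia". A benign lesion could therefore be a malignancy in SAP 8.3.1 but not in the damage index.

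**Arithmetic.** Inputs: 120 subjects randomised 1:1 (Protocol 3.1), so 60 per arm; follow-up to Week 60. Assumptions: every subject has full follow-up, and a year is 52.18 weeks. The event counts are illustrative.

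- One subject: 1/60 = 1.67 percentage points.
- Person-time per arm: 60 × 60 / 52.18 = 69.0 person-years.
- One true malignancy: 1/60 = 1.7%; 1/69.0 = 1.45 per 100 person-years.
- One true malignancy plus a benign event in another subject: 2/60 = 3.3%; 2/69.0 = 2.90 per 100 person-years.
- One true malignancy plus three benign occurrences in one other subject: still 2/60 = 3.3%, but 4/69.0 = 5.80 per 100 person-years.

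**Could benign events alone give a small p-value?** Two-sided Fisher's exact test, 60 per arm, subjects with an event in one arm v none in the other:

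| Split | p |
|---|---|
| 1 v 0 | 1.00 |
| 2 v 0 | 0.496 |
| 3 v 0 | 0.244 |
| 4 v 0 | 0.119 |
| 5 v 0 | 0.057 |
| 6 v 0 | 0.027 |

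It would take a 6 v 0 split, so no claim of false significance is made.

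Protocol 1.4 gives lymphoproliferative disease and skin cancer rates for MMF, but they come from long-term use in solid organ transplantation. They are not used here to size the problem in quiescent SLE over 60 weeks.

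**The case against.** The strongest reply is that broad capture is a deliberate and defensible safety convention. SAP 8.3.1 builds infections in the same way, and an unspecified neoplasm may later prove malignant, so dropping it risks an undercount. That risk is real and the fix has to respect it. It does not justify counting plainly benign lesions under a malignancy label, and broad capture survives if those events have their own row.

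The second reply is that the preferred-term tables, together with the listings planned in SAP 8.1, let a reader pick out the benign terms. This stands as mitigation. It does not correct the headline proportion, rate, Fisher test or Poisson comparison.

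Some of the supporting comparisons are weaker than the main point. The SLICC/DI measures irreversible damage, so its malignancy item need not match an adverse-event endpoint. Protocol 5.4.1 is a toxicity-management section that also covers other malignancies, and it does not define the endpoint. Silence in SAP section 12 is not itself a defect, since the protocol gave no derivation to depart from. The case rests on SAP 8.3.1 alone.

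Finally, no consequence has been demonstrated: the event counts above are assumed, the rule is the same in both arms, and all safety p-values are declared exploratory. That is correct and limits the weight of the point.

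**Conclusion.** The concern holds. Followed exactly, SAP 8.3.1 places non-malignant events in an endpoint called All malignancies, and no other text prevents it. This follows from the wording and needs no assumption.

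Its effect depends on whether any treatment-emergent benign or unspecified event of Grade 2 or higher is coded to this SOC. With none, nothing changes. Otherwise, at 60 per arm with full follow-up, each additional subject with only such an event adds 1.7 percentage points to the arm's proportion, and each occurrence adds 1.45 events per 100 person-years. The likely number of such events cannot be estimated from the documents.

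The consequence is modest. The endpoint is one of nine exploratory safety endpoints, its composition will be visible, and neither the primary analysis nor the safety triggers in Protocol 5.10.3 use it. The definition should still be corrected, because the error is certain and the change is small.

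**What to change.** Redefine the endpoint in SAP 8.3.1 as (a) adverse events marked Yes on the CRF malignancy question, plus (b) events coded to the neoplasm SOC whose preferred term is confirmed malignant on treatment-blind review. Tabulate the remaining benign and unspecified events in that SOC, by arm, in a separate row labelled as such. An unspecified lesion that the investigator called malignant still counts, and one that cannot be settled stays visible. State that the malignancy indicator in SAP 8.3 follows the same definition.

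The cost is a few lines of SAP text and a short review of one SOC's preferred terms. The CRF answer and the preferred terms are already collected. The SAP already plans a comparable step for medications in 7.3.8: "A blinded list of study medications will be reviewed to identify the addition of aggressive adjunctive therapy or cytotoxic drugs". It also has a masked panel for protocol deviations in 4.3. One practical point: Protocol 3.1.1 leaves the coordinating centre's statistical and project staff and the sponsor's medical monitor unblinded, so the review needs someone without access to treatment assignments.

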#### 7.3.3 Collecting Adverse Events

Adverse events (including SAEs) may be discovered through any of these methods:

• Observing the subject.

- Questioning the subject in an objective manner.
- Receiving an unsolicited complaint from the subject.
- In addition, an abnormal value or result from a clinical or laboratory evaluation (including, but not limited to, a radiograph, an ultrasound, or an electrocardiogram) can also indicate an adverse event, as defined in Section 7.4, *Grading and Attribution of Adverse Events*.

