# 8.3.1 Safety Analysis

All safety analyses will be performed using the Safety Population.

AEs including changes in laboratory values will be graded according to the National Cancer Institute's *Common Terminology Criteria for Adverse Events (CTCAE) Version 4.0* (http://ctep.cancer.gov/reporting/ctc.html). The frequency of AEs will be summarized by system organ class, preferred term, severity (grade), and relationship to study treatment. Relationship to study treatment will be categorized as either treatment related (possibly, probably, or definitely related to study medication) or unrelated (unlikely related or unrelated). Similar analyses will be performed for SAEs. To account for differential duration of study participation among subjects, the summaries will include the event rate (i.e. number of events per person-time) in addition to the number and percent of events and subjects experiencing events.

For each key safety endpoint defined in Section 3.3.2, *Secondary Safety Endpoints* the proportion of subjects experiencing at least one event in each treatment group will be reported and the treatment groups compared based on Fisher's Exact Test. In addition, event rates in the two arms will be compared using Poisson regression.

Laboratory parameters will be summarized both overall and by treatment group using appropriate descriptive statistics. For each lab parameter, the number and percent of subjects that have an increase, decrease, or no change from baseline to Week 60 will be displayed for each treatment group and pooled across treatment arms. For parameters with an explicit NCI-CTCAE grading criterion, change from baseline will be indicated by a change in grade. For

parameters that do not have an explicit NCI-CTCAE, observed values will be categorized as 'high' (defined as >ULN) and 'normal' (defined as  $\leq$  ULN). Then, a change from baseline will be indicated as a change in category

[figure not shown]
All safety comparisons and associated p-values are considered exploratory, not as formal tests of hypothesis. As such, no adjustments will be made for multiple comparisons and all p-values must be interpreted cautiously.

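### Grade 3-5 hematological events are identified by one MedDRA organ class alone, so a low-count AE coded to another class drops out of that safety endpoint

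*SAP*

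**What the plan says.** SAP 8.3.1 lists nine secondary safety endpoints. The seventh is "All NCI-CTCAE Grade 3-5 hematological events". Further down, the section defines the cases: "Hematological events will include AEs that are coded to the SOC of" Blood and lymphatic system disorders. Nothing else qualifies an event.

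The two paragraphs before it handle infections and malignancies differently. Each takes the matching organ class (SOC) and then adds events flagged on the case report form, "along with any AE with an answer of Yes to the question" about that category. SAP 8.3 confirms the contrast: "Indicator variables will be derived for the following categories of AEs: infections, malignancies, BILAG A flares, and severe SELENA-SLEDAI flares". No hematological indicator is listed.

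The protocol makes laboratory findings a source of AEs. Section 7.3.3 says that "an abnormal value or result from a clinical or laboratory evaluation" can indicate one. Section 7.4.1 defines a treatment-emergent event, where CTCAE grades the test, as a rise in grade from Day 0 or from the last post-baseline value that was not gradable. Section 7.3.4 has Grade 2 and above recorded. Section 8.3.1 says "AEs including changes in laboratory values will be graded according to" CTCAE version 4.0. Section 5.4.2 looks for hematological toxicity by blood count at every visit, with thresholds for neutrophils, white cells, platelets and hemoglobin.

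For each safety endpoint, SAP 8.3.1 compares the arms by Fisher's exact test on the proportion with at least one event and by Poisson regression on event rates.

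**The concern.** The protocol's hematological event is in essence a laboratory finding, whereas the SAP's is membership of one dictionary class. The two agree only if every Grade 3-5 low-count AE is coded to the Blood SOC. A site may record the same finding as a diagnosis or as a test result. If the dictionary places the second wording elsewhere, the event fails the filter although its grade and clinical content are identical.

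Hematological derangement is one of the harms that the protocol sets against flare risk (1.5 and 8.3.2.1), and 1.5.4 says the control arm is there partly to compare toxicities on and off MMF. An endpoint named for all such events should not depend on a site's choice of words. This category also has the most laboratory-driven detection of the three, yet it is the one without a second route.

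**Working it through.** The plan gives no rate, power or sample size for endpoint 7, so there is no figure to reproduce. The check is a comparison of the texts, followed by an illustration of scale.

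**Following one event through the plan**

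1. A central-laboratory count rises to CTCAE Grade 3. Under Protocol 7.4.1 and 7.3.4 it is an AE and is recorded.
2. It is coded with MedDRA 16.1 (SAP 8.3). If the code falls in the Blood SOC, it enters endpoint 7.
3. If the code falls in any other SOC, SAP 8.3.1 excludes it from endpoint 7 and from that endpoint's Fisher and Poisson comparisons. No flag brings it back.
4. It remains in endpoint 3 (all Grade 3-5 AEs), in endpoint 2 if attributed to MMF, and in the SOC and preferred-term tables of SAP 8.3.
5. SAP 8.5 plots laboratory data by arm and overlays subjects with Grade 2 or higher values, but does not count them. The grade-shift table in Protocol 8.3.1 is not in SAP 8.5, and SAP Section 12 does not list its omission. That table compares only baseline with Week 60, so a mid-study drop that recovered would not show in it.

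**Effect of losing a share of events**

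Let *s* be the share of true cases coded to another SOC, assumed equal in both arms. The documents do not give *s*. With true risks p1 and p2:

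- observed difference = (p1 − p2)(1 − s), which shrinks towards zero;
- observed ratio = p1(1 − s) / p2(1 − s) = p1/p2, which is unchanged.

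If *s* differs between arms, the ratio shifts as well. In every case the count can only fall.

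**Scale**

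The only related rate in the documents is 2% to 3.6% for severe neutropenia in transplantation (Protocol 1.4). It covers one cell line in another population, so it only indicates the order of magnitude. With 120 randomized 1:1, take n = 60 on MMF. Expected counted cases = 60 × p(1 − s); chance of counting none = (1 − p(1 − s))^60.

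| s (assumed) | Expected cases, p = 2% | Expected cases, p = 3.6% | Chance of none, p = 2% | Chance of none, p = 3.6% |
|---|---|---|---|---|
| 0 | 1.20 | 2.16 | 0.30 | 0.11 |
| 25% | 0.90 | 1.62 | 0.40 | 0.19 |
| 50% | 0.60 | 1.08 | 0.55 | 0.34 |
| 75% | 0.30 | 0.54 | 0.74 | 0.58 |

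For the Fisher comparison (two-sided 0.05, 60 per arm, exact), assumed risks of 10% and 1% give power 0.40, 0.21, 0.06 and 0.003 at s = 0, 25%, 50% and 75%. Assumed risks of 15% and 2% give 0.64, 0.43, 0.19 and 0.02. With equal arms these hold whichever arm has the higher risk. The risks have no source in the documents; the figures show only how sensitive a rare-event comparison is to incomplete capture.

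**The case against.** The strongest reply is that little is lost. Every Grade 3-5 AE is tabulated by SOC, preferred term and arm under endpoint 3, so a reader can find low-count terms wherever they sit. Laboratory grades already feed the AE data through Protocol 7.4.1. All safety comparisons are declared exploratory (Protocol 8.3.1, SAP 8.1), and no decision rule rests on endpoint 7. The documents also reproduce neither the MedDRA hierarchy nor the coding conventions, so they cannot show that any event will be coded outside the Blood SOC.

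Most of this stands, and it limits the point to one endpoint and its two comparisons. It does not remove the point: finding the terms by hand in another table is not the pre-specified endpoint, and no test or rate ratio is produced from them.

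A reader might also infer that MMF marrow toxicity is under-counted mainly in the maintenance arm, so that the benefit of stopping MMF is understated. The documents do not support that. Endpoint 7 covers hematological events of any cause. SLE itself lowers counts: the SELENA-SLEDAI scores low platelets and white cells, and a platelet count below 60,000/mm³ and hemolytic anemia are among its severe-flare criteria. Withdrawal could therefore raise such events. The withdrawal arm also takes MMF during the 12-week taper and may receive it again after reactivation. The direction of any bias between arms is open.

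**Conclusion.** The point holds as a gap in the case definition. As written, SAP 8.3.1 leaves a Grade 3-5 low-count AE coded to another SOC out of endpoint 7 and its Fisher and Poisson comparisons, while the protocol regards that finding as an AE. The rule can lower the count but never raise it, and inclusion can turn on site wording.

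The size cannot be fixed from the documents. It depends on the share coded elsewhere, which the sponsor could find by searching its coded AEs for blood-count terms outside the Blood SOC. If that share is zero, nothing changes. If events are as rare as the transplant figure suggests (about one or two in 60), a loss of half would raise the chance of counting none from 0.11-0.30 to 0.34-0.55. That rests on an assumed share and a borrowed rate. Entrants here have had at least one or two years of stable or decreasing MMF and are screened for low counts, so the borrowed rate may not apply.

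**What to change.** Define endpoint 7 as Grade 3-5 AEs in the Blood SOC plus Grade 3-5 AEs with a preferred term on a pre-specified list of low-count terms (hemoglobin, white cells, neutrophils, lymphocytes, platelets) in any SOC. Fix the list before database lock and without reference to treatment arm. Count each subject once for the proportion.

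As a supportive summary, tabulate by arm the subjects whose worst post-Day 0 central-laboratory value is CTCAE Grade 3 or higher and worse than their Day 0 grade. Show lymphocytes separately: lymphopenia is itself among the SLE classification criteria in Protocol Appendix B and could swamp the other cell lines. This table should support the AE-based endpoint, not replace it.

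The cost is a short term list and one extra table. No new data are needed: hematology is drawn at every scheduled, flare and endpoint visit, and SAP 8.5 already needs graded results to choose which subjects to overlay.
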